4.6.3.6. Clinical Laboratory Evaluation

Descriptive summaries at each planned visit, by treatment group, will be provided for the baseline and postbaseline values, and change from baseline values. The associated descriptive summaries will be presented in SI units and CN units. Limits from the performing laboratory will be used to define low and high.

Observed and change from baseline values for each visit may be displayed in plots for participants who have both a baseline and at least 1 postbaseline planned measurement. Baseline is defined in [Table GPHM.4.1](#). Unplanned measurements will be excluded from plots.

A shift table will be provided including unplanned measurements. The shift table will include the number and percentage of participants within each baseline category (minimum value is low, normal, high, or missing) versus each postbaseline category (minimum value is low, normal, high, or missing) by treatment. The Fisher's exact test will be used to compare percentages of participants who shift from normal/high to low between treatments.

For qualitative laboratory analytes, the number and percentage of participants with normal and abnormal values will be summarized by treatment.

A listing of abnormal findings will be created for laboratory analyte measurements, including qualitative measures. The listing will include participant identification, treatment group, laboratory collection date, study day, analyte name, and analyte finding.

The MMRM model, or ANCOVA (if the MMRM model is not applicable), will be used for the analysis during the treatment period for the continuous measurements for selected lab tests.

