##### **9.4.4.4.4. *Central Laboratory Measures, Vital Signs, and Electrocardiograms***

Actual values and change from randomization to post randomization values of central laboratory measures, vital signs, and selected ECG parameters will be summarized at each scheduled visit. Change from randomization to post randomization value will be summarized for participants who have both a randomization and at least 1 post randomization result.

The percentages of participants with TE abnormal, high, or low measures (including laboratory, vital, and ECG parameters) at any time will be summarized and compared between treatment groups using Fisher's exact test.

The analysis details will be provided in the SAP.

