Summary statistics for categorical measures (including categorized continuous measures) will include sample size, frequency, and percentages. Logistic regression will be used to examine the treatment difference in binary efficacy outcomes if there is a need to adjust for covariates. Otherwise, Fisher's exact test will be used to examine the treatment difference in categorical outcomes.

Summary statistics for discrete count measures will include sample size, mean, SD, median, minimum, and maximum.

For some specific safety-related parameters, the definition of baseline and postbaseline for the double-blind period is specified in [Table GPHM.4.1](#).

The definition of baseline and postbaseline during the intensive lifestyle modification lead-in period can be found in Appendix 4 (Section [6.4](#)).

Table GPHM.4.1. Baseline and Postbaseline Definitions for Safety Groups

Analysis Set	Analysis Type	Baseline	Postbaseline
SS	1.1) Treatment-emergent adverse events	The baseline period is defined as ongoing at the time of the first dose of study drug in the double-blind treatment period.	Starts after the first dose of study treatment and ends at the end of the study period (including off-drug follow-up visit)
SS	1.2) Treatment-emergent abnormal labs ^a , vital signs, and ECGs	The last nonmissing assessment (scheduled or unscheduled) recorded at or prior to randomization to the double-blind treatment period	Postbaseline will be defined as measurements after the randomization visit. All scheduled and unscheduled measurements will be included.
SS	1.3) Change from last baseline to Week xx and to last postbaseline for labs ^a , vital signs, and ECGs	The last nonmissing assessment (scheduled or unscheduled) recorded during the 12-week lead-in period	Postbaseline will be defined as above (1.2). Only scheduled visits will be included. The early discontinuation visits are considered scheduled visits.

Abbreviations: ECG = electrocardiogram; SS = Safety Analysis Set.

^a Immunogenicity-related analysis is specified in Section 4.6.5.6.

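### The SAP's general laboratory shift analysis tests only falls to low; for most other chemistry and all hematology analytes no between-arm comparison of treatment-emergent highs is specified, though the protocol promises one

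*SAP*

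**What the plan says.** Protocol 9.4.4.4.4 makes a commitment in both directions. On the share of people affected, it says: "TE abnormal, high, or low measures (including laboratory, vital, and ECG parameters) at any time will be summarized and compared between treatment groups". The named test is Fisher's exact test. It adds: "The analysis details will be provided in the SAP".

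SAP 4.6.3.6 supplies the laboratory detail. It first states: "Limits from the performing laboratory will be used to define low and high". It then describes a single shift table, which crosses "each baseline category (minimum value is low, normal, high, or missing") with "each postbaseline category (minimum value is low, normal, high, or missing) by treatment". The one between-arm test named for that table is Fisher's exact test on participants "who shift from normal/high to low between treatments".

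Table GPHM.4.1 in SAP 4.1 has a row (1.2) headed "Treatment-emergent abnormal labs", which also covers vital signs and ECGs. It sets the baseline as a single value, the latest one available up to randomization, and counts all scheduled and unscheduled values afterwards. SAP 4.6 names Fisher's exact test as the default for categorical safety responses. SAP 4.9, on departures from the protocol's analyses, does not mention laboratory highs.

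**The concern.** The protocol promises highs and lows; the SAP writes out a rule for lows only. The SAP is explicit about direction elsewhere. Vital signs have a definition of a treatment-emergent high result (4.6.3.4), ECGs have high limits (4.6.3.5), and renal safety pairs a minimum-to-minimum eGFR shift with a maximum-to-maximum UACR shift (4.6.5.11). The general laboratory section has no such high-side counterpart.

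At stake is the routine safety display for analytes where a rise is the worry. Protocol 8.3.2.12 says that gastrointestinal events may lead to dehydration and a decline in renal function. SAP 4.6.5.11 sends renal laboratory measures back to 4.6.3.6, so creatinine, urea nitrogen and cystatin-C enter a table whose only test is for falls. The same holds for potassium, calcium, uric acid and creatine kinase.

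**Working it through.** No sample-size or power figure is involved, so there is no plan figure to reproduce. The check has three steps.

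**1. What a minimum-based category means.** Let L and U be the laboratory's lower and upper limits.

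- Minimum below L: at least one value is low.
- Minimum above U: every value is high.
- Maximum above U: at least one value is high.

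The table therefore records any low but only all-high. The protocol's wording, at any time, corresponds to any low and any high. A participant whose every postbaseline value is high does appear as high, but no test uses that cell.

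**2. How many analytes are affected** (counted from protocol Appendix 2; TSH, FSH and pregnancy tests excluded, UACR counted once).

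| Step | Count |
|---|---|
| Hematology 12 + chemistry 15 + other 15 | 42 |
| Less 8 with a high-side safety analysis: p-amylase, lipase (SAP 4.6.5.1.1); ALT, AST, total bilirubin, ALP (4.6.5.3.3); UACR (4.6.5.11); calcitonin (4.6.5.12.1) | 42 − 8 = 34 (81%) |
| Less 5 with exploratory category shifts on the EAS: LDL-C, HDL-C, triglycerides, fasting glucose, HbA1c (Table GPHM.4.4) | 34 − 5 = 29 (69%) |
| Less eGFR, where low values are the concern | 29 − 1 = 28 (67%) |
| Less creatinine, partly reflected in the eGFR shift | 28 − 1 = 27 (64%) |

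Within chemistry and hematology alone, 27 − 4 = 23 lack a high-side safety analysis (11 of 15 chemistry, 12 of 12 hematology). Crediting glucose and creatinine leaves 21.

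**3. How much a minimum-based table hides.** This is an illustration under assumptions, not from the documents. Values have unit SD and within-person correlation ρ, limits lie at ±1.96 SD, the baseline is normal, there are 4 or 6 postbaseline samples, ρ runs from 0.5 to 0.9, and the mean shift from 0 to 1 SD.

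- Any value high: 2.7% to 46.5% of participants.
- Shown as high by the minimum rule: 0.01% to 7.3%, which is 0.1% to 30% of those with any high value.
- Example with 4 samples, ρ = 0.7 and a shift of +0.5 SD: 15.05% have a high value and 0.70% are shown as high (0.70 / 15.05 = 4.7%). The tested category, any low, holds 1.23%. With no shift, the any-high and any-low figures are 5.18% and 5.22%.

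In the example, the upward shift raises any-high from 5.18% to 15.05%, but the tested quantity only falls, from 5.22% to 1.23%.

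**The case against.** The strongest reply is that the SAP holds most of the pieces. Row 1.2 of Table GPHM.4.1 sets the windows, 4.6.3.6 says whose limits apply, 4.6 gives Fisher's exact test as the default, and the protocol's commitment is never withdrawn. On that view the SAP is under-specified and has spelled out only the low half. This stands in part: it suggests that a two-sided analysis was intended. But a window and a default test do not define a treatment-emergent high laboratory result or name an output, and the one rule that is written runs in one direction.

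Three stronger readings are tempting, and the documents do not support them.

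- *Highs will never be compared.* What can be said is that no such comparison is specified for these analytes. The sponsor may still run it.
- *The trial cannot detect upward laboratory signals.* Visit-by-visit summaries by arm, models for selected tests and a listing of abnormal findings remain (SAP 4.6.3.6). So do the eGFR shift, the acute renal and the dehydration searches (4.6.5.11). Protocol 8.2.4 also requires clinically relevant laboratory changes to be reported as adverse events. A general upward shift could even show as fewer falls to low. None of these, however, compares the proportion of participants with a high value.
- *The sponsor removed the analysis without disclosure.* Protocol 9.4.1 lets changes that are not principal features be described and justified in the SAP or the study report, and SAP 4.9 is framed around objectives. Its silence fits a drafting omission equally well.

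**Conclusion.** The point holds in bounded form. SAP 4.6.3.6 specifies a low-side rule where the protocol commits to both sides, and the difference is neither recorded nor justified. By the count above, 34 of about 42 analytes have no high-side safety analysis, and about 27 remain after every reasonable credit, including all of hematology. The count rests on reading Appendix 2 as listed. The credits are generous, because the lipid, glucose and HbA1c shifts are exploratory, use on-drug data and run from Week 0 to 72 weeks, not at any time. The simulation shows direction and rough scale only.

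A related inconsistency needs settling. The shift table uses a minimum at baseline, while row 1.2 of Table GPHM.4.1 defines one baseline value, which has no separate minimum or maximum.

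This concerns completeness of safety reporting. It does not touch the co-primary or key secondary conclusions, and the liver, pancreatic, calcitonin and albuminuria questions already have their own high-side analyses. It should be corrected.

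**What to change.** - Add to SAP 4.6.3.6 a treatment-emergent high analysis for quantitative analytes: low or normal at baseline, maximum postbaseline value above the upper limit, scheduled and unscheduled values included, arms compared by Fisher's exact test. The vital-sign definition in 4.6.3.4 can serve as a model.
- Keep the minimum-based analysis for shifts to low.
- State one baseline rule for both directions: either the last nonmissing value of Table GPHM.4.1 row 1.2, or a baseline-period maximum for highs and minimum for lows. Amend row 1.2 or 4.6.3.6 so that they agree.
- If the sponsor prefers not to compare highs for some analytes, record that with the reason in SAP 4.9.

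The cost is SAP wording and one further standard table. No new data are needed.

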4.6.4. Patient Narratives

The following are “notable” events, from start of study drug through the end of study participation:

- deaths
- SAEs
- permanent discontinuations of study treatment due to AEs, and
- pregnancies.

Patient narratives (participant-level data and descriptive paragraphs) will be provided for participants in the enrolled population with at least 1 notable event.

4.6.5. Special Safety Topics

For AEs of special interest (AESI) or special safety topics, the counts and percentages of participants will be summarized by treatment and PT with decreasing frequency. Individual participant-level data may be presented. Displays with individual participant-level data may be created using various formats, such as a customized listing and/or a customized graphical patient profile. Adverse events of special interest are defined in each section of special safety topics, where applicable.

4.6.5.1. Exocrine Pancreas Safety

4.6.5.1.1. Pancreatic Enzyme

Observed pancreatic enzyme data (p-amylase and lipase) will be summarized by treatment. The counts and percentages of participants with maximum postbaseline pancreatic enzyme values exceeding the following thresholds will be provided by baseline pancreatic enzyme values (\leq upper limit of normal [ULN], $>$ ULN) and postbaseline values ($\leq 1 \times$ ULN, >1 to $\leq 3 \times$ ULN, >3 to $\leq 5 \times$ ULN, >5 to $\leq 10 \times$ ULN, and $>10 \times$ ULN).

An MMRM analysis will be used to analyze each pancreatic enzyme with a log-transformed (postbaseline measure/baseline measure) response variable and treatment, nominal visit, treatment-by-nominal visit interaction as fixed effects.

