Allowable Deviation (days)		±3	±3	±3	±3	±3	±3	±3	±3	±3	±3	±3	±3	±3	±3	±3	±3	±3	±3	±3	±3	±3	±3	±3	±3	±3	±3	±7	±7		±3
Fasting Visit	X	X		X		X		X		X	X	X	X	X	X	X			X			X			X			X	X	X	X
Telephone Visit			X		X		X		X								X	X		X	X		X	X		X	X				
Lifestyle Program Instruction only			X		X		X		X																						
Chemistry panel (includes Cr for eGFR calculation and glucose)	X									X			X			X				X			X			X			X	X	X
	The CKD-EPI equation will be used by the central lab to estimate and report eGFR.																														
Insulin	X									X			X			X			X			X			X			X		X	X
C-peptide	X									X			X			X			X			X			X			X		X	X
Lipid panel	X									X						X													X	X	X
Free fatty acids	X									X						X												X	X	X	
Serum pregnancy	X									X																					
	For women of childbearing potential only.																														
Urine pregnancy (local)										X			X			X			X			X			X			X		X	
	A urine pregnancy test must be performed at Visit 10 with the result available prior to first injection of study drug(s) for women of childbearing potential only. Additional pregnancy tests (beyond those required by the SoA) should be performed at any time during the trial if a menstrual period is missed, there is clinical suspicion of pregnancy, or as required by local law or regulation.																														
Follicle-stimulating hormone test	X																														
	Follicle-stimulating hormone test is to be performed at Visit 1 for postmenopausal women at least 40 years of age with an intact uterus, not on hormone therapy, and who have had spontaneous amenorrhea for more than 1 year without an alternative medical cause.																														
Calcitonin	X									X			X			X												X		X	X
Pancreatic amylase	X									X			X			X												X		X	X
Lipase	X									X			X			X												X		X	X
Urinary albumin/creatinine ratio	X									X						X												X		X	X
Cystatin-c	X									X						X												X		X	X

Visit	1	2	3	4	5	6	7	8	9	10	11	12	13	14	15	16	17	18	19	20	21	22	23	24	25	26	27	28	99	ED	801		
Week of Treatment	-14	-12	-11	-10	-9	-8	-6	-4	-2	0	4	8	12	16	20	24	28	32	36	40	44	48	52	56	60	64	68	72	72		4 wks Post TxP		
Allowable Deviation (days)		±3	±3	±3	±3	±3	±3	±3	±3	±3	±3	±3	±3	±3	±3	±3	±3	±3	±3	±3	±3	±3	±3	±3	±3	±3	±3	±7	±7		±3		
Fasting Visit	X	X		X		X		X		X	X	X	X	X	X	X			X			X			X			X	X	X	X		
Telephone Visit			X		X		X		X								X	X		X	X		X	X		X	X						

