## 6.3. Measures to Minimize Bias: Randomization and Blinding

This is a double-blind, randomized study.

Participants who meet all criteria for enrollment will undergo a 12-week intensive lifestyle modification lead-in period. Those who achieve  $\geq 5.0\%$  weight loss at Visit 10 will be randomized to one of the study treatment groups (tirzepatide MTD or placebo) for the duration of the treatment period. Assignment to treatment groups will be determined by a computer-generated random sequence using an IWRS. Participants will be randomized in a 1:1 ratio to receive tirzepatide MTD or placebo.

The randomization will be stratified by country, sex (female, male), and percent weight loss at the end of lead-in ( $<10\%$  versus  $\geq 10\%$ ).

Investigators, site staff, clinical monitors and participants will remain blinded to the treatment assignments until the study is complete.

Emergency unblinding for AEs may be performed through the IWRS. This option may be used ONLY if the participant's well-being requires knowledge of the participant's treatment assignment. All emergency unblinding events are recorded and reported by the IWRS.

If an investigator, site personnel performing assessments, or participant is unblinded, the participant must be discontinued from the study. In cases where there are ethical reasons to have the participant remain in the study the investigator must obtain specific approval from a Lilly clinical research physician (CRP) for the participant to continue in the study.

In case of an emergency, the investigator has the sole responsibility for determining if unblinding of a participant's treatment assignment is warranted for medical management of the event. The participant's safety must always be the first consideration in making such a determination. If a participant's treatment assignment is unblinded, Lilly must be notified immediately. If the investigator decides that unblinding is warranted, it is the responsibility of the investigator to promptly document the decision and rationale and notify Lilly as soon as possible.

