4.6. Safety Analyses

Unless specified otherwise, safety assessments for the double-blind period will be based on the SS (Table GPHM.3.1). All data collected between randomization and the end date of study participation will be included, regardless of the adherence to study drug.

Safety outcomes during the intensity lifestyle modification lead-in period will also be summarized for all enrolled participants. Detailed analyses can be found in Appendix 4 (Section 6.4).

The statistical assessment of homogeneity of the distribution of categorical safety responses between tirzepatide and placebo will be conducted using Fisher's exact test, unless specified otherwise.

The mean change from baseline differences among treatments at all scheduled visits will be assessed via an MMRM using REML. Unless specified otherwise, if the safety parameter is assessed at 72 weeks, then the model will include country/pooled country, sex, percentage of body weight reduction at the end of lead-in ($<10\%$ and $\geq 10\%$), treatment group, visit, and treatment-by-visit interaction as fixed effects and baseline value of the safety parameter as a covariate. To model the covariance structure within participants, the unstructured covariance matrix will be used. If this model fails to converge, the covariance structures specified in Section 4.3.2.2 will be tested in order until convergence is met. If the data do not warrant the MMRM model, then an ANCOVA model will be conducted.

For selected parameters, time-to-first-event analysis via the Cox proportional hazards model may be conducted. Participants without the event will be censored at the end of study participation.

For participants experiencing the event, the “time-to-first-event” will be the time (in weeks) from first dose to first occurrence of the event.

Where necessary, the rate of events will be analyzed using a generalized linear mixed model, assuming the number of events follows a negative binomial distribution, with treatment as a fixed effect. The logarithm of days during the active treatment period will be adjusted as an offset, to account for possible unequal treatment duration of follow-up between participants.

Unless otherwise specified, all the analyses listed in this section will be conducted using up to 72 weeks treatment period, plus the safety follow-up (Visit 801), for all randomized participants.

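### The pancreatic enzyme MMRM leaves out, without a stated reason, the baseline covariate and randomization strata of the SAP's general safety model, at a modest cost in precision

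*SAP*

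**What the plan says.** SAP Section 4.6.5.1.1 (Pancreatic Enzyme) fits an MMRM to each enzyme "with a log-transformed (postbaseline measure/baseline measure) response variable". The listed terms are "treatment, nominal visit, treatment-by-nominal visit interaction as fixed effects". No covariate or stratification factor is named.

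SAP Section 4.6 (Safety Analyses) sets the default for mean-change safety comparisons. It opens "Unless specified otherwise, if the safety parameter is assessed at 72 weeks" and continues "then the model will include country/pooled country, sex, percentage of body weight reduction at the end of lead-in". It ends with "treatment group, visit, and treatment-by-visit interaction as fixed effects and baseline value of the safety parameter as a covariate". SAP Section 4.1 and Protocol Section 9.4.1 likewise name stratification factors and baseline for continuous measures over time.

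The three factors in Section 4.6 are the randomization strata. Protocol Section 6.3: "The randomization will be stratified by country, sex (female, male), and percent weight loss at the end of lead-in".

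**The concern.** Dividing by baseline is not the same as adjusting for it. On the log scale the ratio subtracts the whole of log baseline, which is the best use of baseline only if the follow-up value moves one-for-one with it. Where the slope is below 1, the change score over-corrects and carries extra baseline noise into the treatment contrast. A covariate lets the data estimate the slope.

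The shorter list also differs from its neighbours. Vital signs (SAP 4.6.3.4) and ECG heart rate and PR interval (SAP 4.6.3.5) are referred to the Section 4.6 model. Lipids and fasting insulin (Table GPHM.4.3) are log-transformed too, yet use the Section 4.3.2.2 model, which has country, sex and a baseline covariate. The log scale alone therefore does not explain the shorter list.

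At stake is the width of the interval for the between-arm enzyme ratio. In a safety comparison, lost precision makes a real shift harder to see.

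**Working it through.** **The plan's own figure.** None is stated for this model. The power statement in SAP Section 5 concerns the body-weight endpoints and does not depend on this point.

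**Does the Section 4.6 default reach the enzymes?** In the Schedule of Activities (Protocol 1.3), pancreatic amylase and lipase are drawn at Visits 1, 10, 13, 16 and 28 (Week 72), at early discontinuation and at Visit 801. The 72-week condition is met, so the default would apply if Section 4.6.5.1.1 gave no list of its own.

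**Algebra of the response.** log(post/baseline) = log(post) − log(baseline), so the baseline coefficient is fixed at 1.

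**Variance, general case.** Take one visit and complete data, with s0 and s1 the log-scale SDs at baseline and follow-up and rho their correlation (none of these is in the documents).

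- Change score, no covariate: s0² + s1² − 2·rho·s0·s1
- Same response with log baseline as covariate: s1²(1 − rho²)
- Difference: (s0 − rho·s1)², which is never negative. It is zero only when the slope rho·s1/s0 equals 1.

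**Equal SDs (assumed, s0 = s1 = s).** The variances become 2(1 − rho)s² and (1 − rho²)s². Their ratio is (1 + rho)/2, so the reduction is (1 − rho)/2. Intervals as written are wider by √(2/(1 + rho)) − 1. An effect with 80% power under the adjusted model has power Φ[(1.960 + 0.842)·√((1 + rho)/2) − 1.960] as written, at two-sided 0.05.

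| rho (assumed) | Change-score variance / s² | Adjusted variance / s² | Variance reduction | Interval wider by | Power as written |
|---|---|---|---|---|---|
| 0.5 | 1.00 | 0.75 | 25% | 15.5% | 68% |
| 0.6 | 0.80 | 0.64 | 20% | 11.8% | 71% |
| 0.7 | 0.60 | 0.51 | 15% | 8.5% | 73% |
| 0.8 | 0.40 | 0.36 | 10% | 5.4% | 76% |
| 0.9 | 0.20 | 0.19 | 5% | 2.6% | 78% |

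**Simulation check.** With 225 per arm (300 × 0.75, using the 25% dropout in SAP Section 5), no true effect, an assumed log-scale SD of 0.5 and 4,000 replicates, the adjusted-to-unadjusted SE ratios were 0.857, 0.926 and 0.952 at rho 0.5, 0.7 and 0.8. Theory gives 0.866, 0.922 and 0.949. The mean estimate from either model was within 0.001 of zero, so neither is biased.

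**Unequal SDs.** At rho = 0.8 and s1 = 1.25·s0, the slope is 0.8 × 1.25 = 1 and the gain is (1 − 1)²·s0² = 0. The table is therefore not a bound.

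**Strata.** If the strata explain a share R² of the residual variance, omitting them widens intervals by 1/√(1 − R²) − 1: 0.5%, 1.0%, 2.6% and 5.4% at assumed R² of 0.01, 0.02, 0.05 and 0.10.

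**The case against.** The strongest reply is that Section 4.6 is only a default and Section 4.6.5.1.1 overrides it. Protocol Section 9.4.1 also allows other methods to be detailed in the SAP. That stands. A reader might infer a breach of the plan, and the documents do not support that.

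A reader might also infer that the model ignores baseline. It does not, because baseline is the denominator of the response. Only the separate covariate is missing. The list names fixed effects only, while Section 4.6 names baseline separately as a covariate, so the sentence may be shorthand. That reading is weaker for the strata, which Section 4.6 does call fixed effects. Either way, two programmers could fit different models, and one line would settle it.

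A third tempting inference is bias through regression to the mean. The exclusion criteria (Protocol 5.2) set no amylase or lipase threshold, and randomization makes any regression to the mean equal between arms in expectation. A chance baseline imbalance is variation that the standard error already reflects. The loss is of precision only.

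Finally, a reader might link this to the pancreatitis conclusion. SAP Section 4.6.5.1.2 bases that event of special interest on adjudication-confirmed cases. The threshold table in Section 4.6.5.1.1 is already split by baseline category and does not use this model. Protocol Section 8.3.2.2 itself gives serial enzymes little predictive value in asymptomatic patients. This limits the importance of the point. It gives no reason to prefer the less precise model for a comparison the sponsor has chosen to run.

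**Conclusion.** The point holds as a small, free gain in precision and an unexplained inconsistency within the SAP. The planned contrast is valid and unbiased under randomization with complete data. For a visit taken on its own, adjusting for log baseline cannot increase its large-sample variance and usually reduces it.

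The size rests on assumptions: equal log-scale SDs and a correlation that the documents do not give. Over rho 0.6 to 0.8, intervals as written are about 12% to 5% wider than they need be. The gain could be larger or smaller with unequal SDs, and is nil at a true slope of 1. The strata matter less unless they explain more of the enzyme variation than seems likely.

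The analysis is supportive and outside the multiplicity scheme (SAP 2.1), and no stated decision depends on it.

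**What to change.** In SAP Section 4.6.5.1.1, add log baseline enzyme as a covariate, and country/pooled country, sex and lead-in weight-loss category (<10%, ≥10%) as fixed effects, to match Section 4.6. Alternatively, state why they are left out. With log baseline in the model, the log-ratio response can stay: the treatment estimate is the same as with log postbaseline as the response.

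The cost is one sentence of SAP wording and the matching program change, best made before unblinding. Baseline enzymes are drawn at Visit 10 and the strata are known at randomization, so no new data are needed.
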